### 3 INTRODUCTION

## 3.1 Idiopathic Pulmonary Fibrosis

Idiopathic pulmonary fibrosis (IPF) is a chronic, progressive, and fatal lung disease of unknown cause that is characterized by worsening dyspnea, cough, and progressive loss of lung function due to scar formation in the lung. IPF belongs to a family of lung disorders known as interstitial lung diseases (ILDs) and is characterized by the pathological and radiographic pattern known as usual interstitial pneumonia (UIP). A diagnosis of IPF is diagnosis of exclusion, as it is reserved to those individuals with the UIP pattern of lung injury without any identifiable cause such as connective tissue disease or environmental exposure. It is a progressive disease in which scarring and lack of elasticity in the lung continues to increase until the majority of patients die from respiratory failure. Non-drug treatments include supplemental oxygen, pulmonary rehabilitation, and lung transplant.

To date, 2 drugs have been approved for treatment of IPF in several countries globally: pirfenidone, a small-molecule inhibitor of fibrosis (precise mechanism of action is unknown), and nintedanib, a triple tyrosine kinase inhibitor, that blocks signaling from vascular endothelial growth factor, fibroblast growth factor-, and platelet-derived growth factor receptors. In separate Phase 3 trials in IPF patients, both pirfenidone and nintedanib slowed the rate of decline in forced vital capacity (FVC). In addition, nintedanib significantly improved respiratory related quality of life. Both drugs have significant gastrointestinal side effects, many patients progress despite treatment and as such, there remains a significant unmet need based on the benefits and risks of the approved treatments.

# 3.1.1 Non-IPF, Progressive Fibrotic ILD (PF-ILD)

Beyond IPF, some patients with other chronic forms of fibrotic ILD develop a progressive phenotype characterized by worsening respiratory symptoms, lung function, progressive fibrosis on imaging and early mortality. There is a high unmet need for effective and tolerable treatments for patients with PF-ILD that exhibit disease progression. Because of the clinical and pathophysiological similarities among these diseases, it has been suggested that such disorders have a common pathobiologic mechanism regardless of the cause – with resultant progressive lung fibrosis – and thus could have a response to similar treatment as IPF. Indeed, in the recently published INBUILD trial, patients with PF-ILD with diverse etiologies were treated with nintedanib vs placebo. Those treated with nintedanib had slower progression of lung fibrosis than those who received placebo, as demonstrated by a lower annual rate of decline in FVC over the 52-week study period. The absolute treatment effects in this PF-ILD cohort were similar in magnitude to those observed in the pivotal INPULSIS trials that led to approval of nintedanib for treatment of IPF and based on data from the INBUILD trial, a number of health authorities have also approved nintedanib for patients with PF-ILD.

# 3.2 Lysophosphatidic Acid Receptor Pathway

Aberrant wound healing responses to lung injury are widely assumed to contribute to the pathogenesis of fibrotic lung diseases, such as IPF. Lysophosphatidic acid (LPA), by virtue of its ability to mediate many basic cellular functions in several cell types associated with wound healing

(survival/apoptosis, proliferation, migration, and contraction), can regulate the transition from normal scar formation to aberrant wound repair (fibrosis), which is characterized by excessive deposition of extracellular matrix. LPA mediates its physiological effects by binding to and activating a family of G protein-coupled receptors (LPA1-6).

Several lines of published evidence support targeting the LPA/lysophosphatidic acid receptor subtype 1 (LPA1) receptor pathway in fibrotic diseases and for the treatment of IPF. Increased LPA concentrations have been reported in the alveolar space of both IPF patients and the corresponding bleomycin (BLEO) mouse lung model, in which genetic deletion or pharmacological inhibition of LPA1 attenuated the development of the modeled disease, suggesting a direct involvement of LPA and LPA1 in disease pathogenesis. Increased epithelial cell apoptosis in response to lung injury has also been implicated in the development of IPF and linked to LPA. LPA signaling through LPA1 has been reported to promote epithelial cell apoptosis induced by BLEO injury in mice. The number of apoptotic cells present in the alveolar and bronchial epithelia of LPA1-deficient mice was significantly reduced compared with wild-type mice after BLEO challenge.

Consistent with these in vivo rodent results, increases in LPA levels and LPA signaling through LPA1 have been observed in individuals with fibrotic diseases. LPA levels are elevated in the bronchoalveolar lavage (BAL) of patients with IPF. Increased concentrations of autotaxin, the enzyme largely responsible for extracellular LPA production, have been found to be elevated in both murine and human fibrotic lungs. Together these data suggest that antagonizing the LPA1 receptor may be beneficial in treating patients with IPF. Furthermore, a previous Phase 2 study demonstrated improvements in the rate of decline in lung function (as measured by FVC) in IPF patients treated with the LPA1 antagonist BMS-986020 compared to placebo.

BMS-986278 is a potent full antagonist at LPA1 that has been shown to potently inhibit LPA-stimulated activation of multiple signal transduction pathways. BMS-986278 is being developed as a potential treatment for IPF (see the Investigator's Brochure for additional details).

# 3.3 Study Rationale

A clinical need exists for more effective treatment of pulmonary fibrosis. Nonclinical studies support the development of BMS-986278 as a potential treatment for IPF by its antagonistic effect on LPA1. The overall objective of the clinical development program is to demonstrate that BMS-986278 is effective and safe for the treatment of IPF.

A separate cohort of PF-ILD, will also be enrolled to evaluate whether BMS-986278 is safe and efficacious for the treatment in PF-ILD.

In order to augment knowledge about safety, tolerability, and efficacy of BMS-986278, an optional treatment extension (OTE) will be offered to those participants that complete the 26-week main study.

The proof of concept for antifibrotic activity with an LPA1 antagonist was demonstrated in a randomized, double-blind, placebo-controlled Phase 2 study with BMS-986020, another selective,

small-molecule LPA1 antagonist (Study IM136003) discussed below in Section 3.4.4.1. The present study is designed to provide an initial evaluation of the efficacy of BMS-986278, further demonstrate the safety and the tolerability of BMS-986278 and provide information on the pharmacokinetics of BMS-986278 in participants with IPF and in those with PF-ILD. In this study, it is anticipated that the average rate of decline in percent predicted forced vital capacity (ppFVC) between baseline and Week 26 will be smaller among participants taking 1 of the 2 different doses of BMS-986278 than among those taking placebo.

#### 3.4 Background

Details on the nonclinical pharmacology, pharmacokinetics (PK), and toxicology of BMS-986278 are in the Investigator's Brochure.

# 3.4.1 Nonclinical Pharmacology

See the Investigator's Brochure for additional details on nonclinical pharmacology studies.

BMS-986278 is a potent full antagonist of LPA1 (Kb = 6.9 nM). BMS-986278 potently inhibited LPA-stimulated activation of multiple signal transduction pathways mediated by G protein-coupled receptors Gq, Gi, and G12, as well as β-arrestin recruitment in heterologous cells and endogenous cells expressing human LPA1 (hLPA1), exhibiting 3.9 to 25 nM affinity in all assays. BMS-986278 also acts as a potent but partial inhibitor of LPA3 (Kb = 2.1 nM, maximal inhibition (Imax) = 36%); however, was inactive at other LPA receptor isoforms tested, including LPA2, LPA4, and LPA5. BMS-986278 is also a potent inhibitor of the mouse and rat LPA1 receptor (Kb = 4 nM), indicating the suitability of these animal species for preclinical efficacy testing. LPA1 signaling has been shown in preclinical studies to contribute to the development of lung fibrosis, in part, through the stimulation of Gq-mediated Ca2+ flux and fibroblast proliferation. BMS-986278 was a potent inhibitor of LPA-stimulated proliferation of human lung fibroblasts with IC50 of 25 nM.

In vivo, BMS-986278 demonstrated antifibrotic efficacy in both the murine subcutaneous bleomycin systemic model as well as in the intratracheal BLEO rat model of lung fibrosis. BMS-986278 administered orally at 10 mg/kg (twice daily [BID] for 14 days, administered starting on Day 7 after BLEO treatment) decreased BLEO-induced fibrosis, as measured by quantitative histological analysis, by 55% (P < 0.01; plasma trough concentration 244 nM; calculated occupancy 87%) in the rat model and by 58% (P < 0.01; plasma trough concentration 239 nM; calculated occupancy 95%) in the mouse model.

Taken together these data suggest that antagonizing the LPA1 receptor with BMS-986278 may be beneficial in treating patients with IPF and with PF-ILD in general.

#### 3.4.2 Nonclinical Pharmacokinetics

See the Investigator's Brochure for additional details on nonclinical PK studies.

The nonclinical PK of BMS-986278 following a single intravenous (IV) or oral dose were characterized in mice, rats, dogs, and monkeys. After IV administration, the apparent elimination half-life (T-HALF) of BMS-986278 was 2.5, 4.5, 5.7 and 11 hours in mice, rats, dogs, and monkeys, respectively. Total plasma clearance was low in monkeys and moderate in other

Protocol Amendment No.: 05

preclinical species (37, 15, 29, and 2 mL/min/kg in mice, rats, dogs, and monkeys, respectively). The steady-state volume of distribution (Vss), ranging from 1.6 L/kg to 5.5 L/kg in mice, rats, dogs, and monkeys, indicated extensive extravascular distribution of BMS-986278. The absolute oral bioavailability was 70%, > 100%, 35%, and 79% in mice, rats, dogs, and monkeys, respectively.

BMS-986278 showed significant metabolic turnover in hepatocytes across species (mouse, rat, dog, monkey, and human). Direct glucuronidation of the carboxylic acid moiety to form an acylglucuronide (BMT-332415) was predominant in dog and monkey hepatocytes, and major in hepatocytes of other species. N-demethylation (BMT-323719) was another major metabolic pathway in human, monkey, and rodent hepatocytes. Oxidation, dealkylation, and epimerization were minor in human hepatocytes.

# 3.4.3 Nonclinical Toxicology

See the Investigator's Brochure for additional details on nonclinical toxicology studies.

# 3.4.3.1 Genotoxicity, Phototoxicity, Safety Pharmacology

Briefly, BMS-986278 is neither genotoxic nor phototoxic. Moreover, the compound has displayed no safety pharmacology concerns based on off-target, central nervous system, respiratory, or electrocardiogram (ECG) assessments. In telemeterized monkeys (Good Laboratory Practice [GLP] study), a single 20 mg/kg dose (highest dose tested), produced transient and minimal decreases in systolic blood pressure (SBP) and mean arterial blood pressure (BP) (7 to 9 mmHg) from approximately 4.5 to 8 hours post dose, a transient increase in heart rate (HR) (6 beats per minute [bpm]) from 2 to 2.5 hours post dose, and a minimal decrease in HR (-14 bpm) from 4.5 to 6.5 hours post dose. These effects were not replicated in a subsequent telemeterized monkey study (non-GLP) at higher doses, 50 and 100 mg/kg. There were no effects noted in any of the cardiovascular parameters (hemodynamics, ECG, rate, rhythm, or waveform morphology). Based on these studies, the monkey may not be predictive of the BP changes observed in humans.

# 3.4.3.2 Repeat-dose Toxicity

In the 1-month oral rat toxicity study, BMS-986278 was well tolerated up to the highest dose tested (300 mg/kg/day) with no BMS-986278-related adverse findings. Therefore, the no-observed adverse effect level (NOAEL) was considered to be 300 mg/kg/day.

In the 6-month oral toxicity study in rats with a 3-month recovery period, BMS-986278 was well tolerated up to the highest dose tested, 300 mg/kg/day (area under the plasma concentration-time curve from time 0 to 24 hours post dose [AUC(0-24h)] = 2,400  $\mu$ g•h/mL in males and AUC[0-24h] = 3,120  $\mu$ g•h/mL in females). The only adverse finding was increased incidence/severity (minimal to moderate) of degenerative joint disease at the femorotibial joint (common age-related spontaneous background change in rats, characterized by articular cartilage fibrillation, clefting, erosion and/or chondrocyte loss/cloning, synovial inflammation, capsular fibrosis without bone changes) in males at  $\geq$  100 mg/kg/day ( $\geq$  AUC[0-24h] = 615  $\mu$ g•h/mL). Therefore, the NOAEL was considered to be 30 mg/kg/day (AUC[0-24h] = 45.2  $\mu$ g•h/mL; males and AUC[0-24h] =

106 μg•h/mL females). Similar findings were not observed in sexually mature monkeys dosed for 9 months up to 150 mg/kg/day (see below).

In the 1-month oral toxicity study in sexually immature monkeys, BMS-986278 was well tolerated up to the highest dose tested (100 mg/kg/day). At 100 mg/kg/day the only noteworthy BMS-986278-related finding was moderate physeal dysplasia, segmented at the caudal aspect of the distal femur in 1 of 5 monkeys assessed with no associated changes in bone biomarkers. The bone change was considered adverse because, in sexually immature monkeys with a continuously growing growth plate, it could potentially result in malalignment of the adjacent articular surfaces before attainment of full sexual maturity. The bone finding is consistent with the role of LPA1 in development of the growth plate and chondrocyte proliferation and positioning to promote cartilage formation. No bone findings were evident in recovery monkeys. Based on the bone findings at 100 mg/kg/day, the NOAEL in sexually immature monkeys was considered to be 50 mg/kg/day (mean sex-combined AUC(0-24h) = 251 µg•h/mL).

In the 9-month oral toxicity study in sexually mature monkeys with a 3-month recovery period, doses tested were 0 (vehicle), 20, 50, or 150 mg/kg/day. BMS-986278 was well tolerated by monkeys up to the highest dose tested with no adverse BMS-986278-related findings. Moderate physeal dysplasia noted in 1/5 females in sexually immature monkeys at 100 mg/kg/day in the 1-month toxicity study did not recapitulate in sexually mature monkeys (with closed growth plates). Therefore, the NOAEL was considered 150 mg/kg/day (mean sex-combined AUC[0-24h] = 1,140•μg·h/mL).

# 3.4.3.3 Embryo-fetal Development Studies

Embryo-fetal development studies in rat and rabbit indicated that BMS-986278 is a selective developmental toxicant. In pregnant rats, BMS-986278 was administered orally at 0, 15, 45, and 75 mg/kg/day during the period of organogenesis (Gestation Day [GD] 6 to 16). Fetal external, visceral, and skeletal malformations, predominantly localized to the craniofacial and thoracic/rib regions were noted starting at the lowest dose tested (15 mg/kg/day; mean AUC[0-24h] = 16 μg•h/mL). The malformations occurred in the absence of any apparent maternal toxicity. In rabbits, BMS-986278 was administered orally at 0, 20, 75, and 200 mg/kg/day during the period of organogenesis (GD 7 to 19). BMS-986278-related effects on maternal survival, body weight (including body weight loss), food consumption (inappetence), and fetal viability (increased postimplantation loss) were observed at 200 mg/kg/day. An increased incidence of fetal skeletal malformations (ribs, sternebrae, cranium/skull) was noted at ≥ 75 mg/kg/day (absence of maternal toxicity at 75 mg/kg/day). In light of these findings, the developmental NOAEL was considered to be 20 mg/kg/day (mean AUC[0-24h] = 32.1 μg•h/mL).

In an oral study of fertility and early embryonic development, BMS-986278 was well tolerated by male and female rats, with no effects noted on fertility or early embryonic development up to doses of 300 mg/kg/day. Therefore, 300 mg/kg/day (BMS-986278 AUC[0-24h] = 1,870  $\mu$ g•h/mL male and 1,390  $\mu$ g•h/mL female) was considered the reproductive NOAEL.

Overall, based on data available to date, the nonclinical safety assessments support continued development of BMS-986278. Evidence for teratogenicity in rats and rabbits highlights the need

for special precautions when enrolling women of childbearing potential (WOCBP) in clinical studies.

# 3.4.3.4 Nonclinical Combination Toxicology

The objective of the clinical development program is to demonstrate that BMS-986278 is safe and effective for the treatment of IPF when used alone or concomitantly with approved IPF treatments. To date, 2 drugs have been approved for treatment of IPF in several countries globally: pirfenidone, a small-molecule inhibitor of fibrosis (precise mechanism of action unknown) and nintedanib (a multiple tyrosine kinase inhibitor).

BMS conducted a definitive 3-month combination toxicity study in rats with BMS-986278 and pirfenidone or nintedanib to determine the potential toxicokinetic and toxicological interactions between the compounds and to support the Phase 2 clinical study. To support the definitive 3-month combination toxicity study dose selection and study design, 2 preceding 7-day dose range-finding studies for BMS-986278 were conducted. Pirfenidone and nintedanib doses were equivalent to the area under the plasma concentration-time curve (AUC) at the maximum recommended human dose (MRHD); pirfenidone 500 mg/kg/day and nintedanib 20 mg/kg/day.

The two 7-day range-finding studies in rats suggested that BMS-986278 exacerbated pirfenidone-induced clinical signs (decreased activity, ataxia, eyelids partially closed, abnormal posture/gait, piloerection, increased/labored breathing, and/or cold to touch). Female animals were more sensitive to the combination effect than the males, resulting in some moribundity at BMS-986278 doses ≥ 15 mg/kg/day in both range-finding studies. The clinical signs/moribundity were partially attributed to observed higher pirfenidone exposures on Day 1. As previously described, rats generally developed tolerability to pirfenidone within 2 to 3 days. Systemic exposure to BMS-986278 was generally lower (< 2×) when coadministered with pirfenidone. Based on range-finding studies, doses in the 3-month study for BMS-986278 doses were decreased to 15/7.5 mg/kg/day (male/female) and pirfenidone dosing was initiated a week prior to BMS-986278 to enable development of tolerance.

Nintedanib and BMS-986278, in combination, was well tolerated in two range-finding studies. In one range-finding study, the observed decrease in nintedanib exposure was attributed to the vehicle. BMS-986278 doses selected for the definitive 3-month combination toxicology study in rat were 30/15 mg/kg/day (male/female) and dosing was initiated concurrently. No PK or toxicological interaction were noted between BMS-986278 and nintedanib.

In a definitive 3-month combination toxicology study, BMS-986278 doses in the pirfenidone combination part of the study were 15 mg/kg/day in males and 7.5 mg/kg/day females (1 to 3× projected high/low human efficacious AUC) and that of pirfenidone was 500 mg/kg/day (1× MRHD). There were no unique clinical pathology or anatomic pathology findings when BMS-986278 was administered in combination with pirfenidone at doses providing clinically relevant exposures. All findings were consistent with those reported previously for each drug alone.  There was a slight increase in alanine aminotransferase (ALT) levels in animals receiving the combination (1.41 to 1.45×). When administered in combination with pirfenidone, BMS-986278 systemic exposures (maximum concentration [Cmax] and AUC[0-24h]) were 0.2 to

Protocol Amendment No.: 05

0.5× those when administered alone, indicating a possible toxicokinetic interaction in rat. Although initiation of pirfenidone dosing 1 week ahead of BMS-986278 enabled development of tolerance to the central nervous system-related signs caused by pirfenidone, clinical signs were observed sporadically in a small number of rats after BMS-986278 administration was initiated on Day 8 in a small number of rats. Additionally, 4 rats were euthanized or found dead on or after Day 45 (3 in the combination group compared to 1 in the pirfenidone alone group). However, when accounting for the different group sizes, there was a similar incidence [5% to 8%] in the combination and pirfenidone-only treatment groups. Nevertheless, the clinical signs and mortality suggested a possible toxicologic interaction between BMS-986278 and pirfenidone.

BMS-986278 doses in the nintedanib combination part of the study were 30 mg/kg/day in males and 15 mg/kg/day females and that of nintedanib was 20 mg/kg/day. There was no toxicokinetic or toxicologic interaction between BMS-986278 and nintedanib when coadministered at doses providing clinically relevant exposures. All findings were consistent with those reported previously for each drug alone.

# 3.4.4 Clinical Experience

# 3.4.4.1 Efficacy of Previous LPA1 Antagonist (BMS-986020)

The proof of concept for antifibrotic activity with an LPA1 antagonist was demonstrated in a randomized, double-blind, placebo-controlled Phase 2 study with BMS-986020, another selective, small-molecule LPA1 antagonist (Study IM136003). Study IM136003 was a 26-week study comparing BMS-986020 600 mg (n=96) to placebo (n=47) in 143 patients with IPF. Study drug was administered either once daily (QD) or BID. The primary endpoint was the rate of change in absolute FVC from baseline to study end, measured at 26 weeks.

For the higher-dose regimen of BMS-986020 600 mg twice daily, the primary treatment comparison, active treatment versus placebo, showed a significant difference in the primary endpoint, change in FVC (liters) from baseline to Week 26. The estimate (95% CI) of the slope of decline in FVC was -0.042 liters (-0.106, 0.022) in the BID group, compared with -0.134 liters (-0.201-0.068) in the placebo group and the difference in estimates of rate of change in FVC from baseline to 26 weeks was 0.093 liters per 26 weeks (0.000, 0.185) (P=0.049). There was no statistically significant difference in slope of FVC decline between BMS-986020 600 mg QD and placebo. The estimate (95% CI) of the slope of decline (liters per 26 weeks) in FVC at Week 26 was -0.073 liters (-0.138,-0.007) in the QD group, compared with -0.134 liters (-0.201,-0.068) in the placebo group and the difference in estimates of rate of change in FVC from baseline to 26 weeks was 0.062 liters per 26 weeks (-0.032, 0.155) (P=0.194).

In Study IM136003, there were 3 drug-associated events of cholecystitis leading to cholecystectomy, and the decision was made to discontinue development of BMS-986020 due to these events. Nonclinical and clinical studies to date with BMS-986278 do not show physiologically significant hepatobiliary effects.

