#### 9.2.5 AEs of Special Interest

AEs of special interest (AESIs) are AEs for a particular product or class of products that a Sponsor may wish to monitor carefully. AESIs may be serious or nonserious. Such events may require further investigation to better characterize and understand them. In the BMS-986278 clinical development program, certain *asymptomatic* and *symptomatic* BP-related AEs are defined as AESIs; however, there has been no definitive assessment on the causal relationship between these events and treatment with BMS-986278. Additional information about *asymptomatic* and *symptomatic* BP-related AEs will be collected on the case report form in order to better characterize and understand them.

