## 9.2.8 Potential Drug Induced Liver Injury (DILI)

Wherever possible, timely confirmation of initial liver-related laboratory abnormalities should occur prior to the reporting of a potential DILI event. All occurrences of potential DILIs, meeting the defined criteria, must be reported as SAEs (see Section 9.2 and APPENDIX 3 for reporting details).

Potential DILI is defined as:

1) Treatment-emergent ALT or AST >  $3 \times$  ULN (>  $2 \times$  baseline AND >  $3 \times$  ULN for participants with baseline elevation),

AND

2) Total bilirubin  $> 2 \times$  ULN ( $> 2 \times$  baseline AND  $> 2 \times$  ULN for participants with baseline elevation) or clinical jaundice, without initial findings of cholestasis (elevated serum alkaline phosphatase),

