#### 10.4.3 Safety Analyses

Analyses of safety data will be based on the safety set, which is defined as all participants who take at least 1 dose of study treatment.

Treatment-emergent AEs and study drug-related AEs and SAEs will be summarized using counts and percentages of participants experiencing the event as well as the number of events by system organ class, preferred term, and treatment group. Physical examination findings, vital signs, clinical laboratory test results, and ECG test results will be summarized using descriptive statistics (n, mean, standard deviation, median, minimum, and maximum) for continuous variables and frequency distributions (counts and percentages) for categorical variables.

The proportions of participants in each treatment group who discontinue study treatment due to changes in BP will be summarized using descriptive statistics.

The PF-ILD cohort will be analyzed separately from the primary study cohort of IPF.

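### Gallbladder events ended the predecessor's development, but the plan has no gallbladder or biliary AESI and no grouped summary across doses and cohorts

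*Combined protocol and SAP*

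**What the plan says.** - **Section 3.4.4.1 (predecessor).** The 26-week IPF study was described as "comparing BMS-986020 600 mg (n=96) to placebo (n=47) in 143 patients with IPF". It had "3 drug-associated events of cholecystitis leading to cholecystectomy, and the decision was made to discontinue development of BMS-986020" because of them. The section then states: "Nonclinical and clinical studies to date with BMS-986278 do not show physiologically significant hepatobiliary effects".
- **Sections 3.4.4.2 to 3.4.4.4 (human exposure so far).** These are healthy-participant studies: up to 14 days of repeat dosing, and single-dose interaction studies with rifampin and pirfenidone. Section 5.4 calls the present study the first evaluation in pulmonary fibrosis. Treatment lasts 26 weeks, plus an optional 26.
- **Section 9.2.5 (AESIs).** Certain "BP-related AEs are defined as AESIs". No other event type is listed.
- **Section 9.2.8 (potential DILI).** This requires raised ALT or AST together with raised bilirubin or jaundice "without initial findings of cholestasis".
- **Section 10.4.3 (safety tables).** AEs and SAEs are counted "by system organ class, preferred term, and treatment group", and the PF-ILD cohort is analyzed separately. No combined-dose column and no grouping of terms is described. Section 10.4.4 presents the extension separately, in five treatment-history groups.
- **Section 3.5 (benefit/risk).** It discusses blood pressure, bone and reproductive toxicity, but not the gallbladder.

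**The concern.** The sponsor relies on the predecessor for proof of concept (Section 3.3) and for dose selection (Section 5.5), but plans no targeted look at the event that ended it. The reassurance for BMS-986278 rests, in humans, on dosing far shorter than the 26 weeks in which the predecessor events arose.

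If gallbladder or biliary events occur, the tables in Section 10.4.3 would spread them over several preferred terms, two doses and two cohorts. The system organ class row brings terms together again, but mixes biliary with hepatic events and is still shown dose by dose. A handful of related events could then appear as ones and twos. If none occur, the plan has no single line that says so for everyone on active drug.

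**Working it through.** **The plan's own figure.** No safety detection figure is stated. The arm size comes from Table 10 in Section 10.1: 2.5 ± 1.96 × 6.5 × √(2/80) = 2.5 ± 2.01, or 0.49 to 4.51. This matches the table, so 80 per arm was chosen for precision on ppFVC alone.

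**Inputs.** The predecessor had 3 events and 96 active participants (Section 3.4.4.1). Section 5.2 gives 240 IPF and 120 PF-ILD participants, each 1:1:1. That is 80 per IPF arm, 40 per PF-ILD arm, and 160 + 80 = 240 on active drug.

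**Predecessor rate.** 3/96 = 3.125%; Clopper-Pearson 95% CI 0.65% to 8.86%.

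**Expected events and chance of at least 3.** Expected = n × 0.03125. P(X ≥ 3) = 1 − Σ (k = 0 to 2) C(n,k) p^k (1−p)^(n−k).

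For n = 80 the terms for k = 0, 1, 2 are 0.079, 0.204 and 0.259. They sum to 0.542, so P = 0.458.

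| Group | n | Expected | P(≥3) |
|---|---|---|---|
| One PF-ILD dose arm | 40 | 1.25 | 13% |
| One IPF dose arm | 80 | 2.5 | 46% |
| Both IPF dose arms | 160 | 5.0 | 88% |
| All active, both cohorts | 240 | 7.5 | 98% |

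**Splitting by term.** If events also divide evenly over three preferred terms (an assumption), the chance of at least 3 in one term's row is 5% for an IPF dose and 0.8% for a PF-ILD dose.

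**Sensitivity to the rate.**
- At the lower limit (0.65%), P(≥3) is 1.6% (n = 80), 8.7% (160) and 21% (240).
- At the upper limit (8.86%) it is 98% for n = 80 and about 100% for 160 and 240.
- If all three events fell in one regimen of about 48 participants (an assumption; 6.25%), it is 88%, 99.8% and about 100%.

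**Testing.** Two-sided Fisher power at 0.05 for 3.1% versus 0% is 4% (80 v 80), 6.5% (160 v 80) and 34% (240 v 120). The predecessor's 3/96 against 0/47 (placebo zero assumed) gives p = 0.55, so a between-arm test would not have flagged it.

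**Zero events.** The one-sided 95% upper bound is 1 − 0.05^(1/n): 3.7% for n = 80 and 1.9% for n = 160.

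**The case against.** **These events would not be missed.** A reader might infer from the cholestasis wording in Section 9.2.8 that biliary events fall outside serious-event reporting. The documents do not support that. The wording limits only potential DILI. Under Appendix 3, cholecystitis with inpatient admission is an SAE, and one needing surgery can qualify as an important medical event. Alkaline phosphatase and bilirubin are in Table 5, and Table 1 schedules laboratory samples at every visit except the conditional Day 2. A DMC reviews safety (Section 5.1.5). All of this stands, so the point concerns targeted collection and summary only.

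**The detail may sit elsewhere.** Section 10.4 calls itself a summary and defers specifications to the SAP. Neither a separate detailed SAP nor the DMC Charter is in the supplied document, so only absence here can be asserted. AESIs, however, are set in Section 9.2.5, and that gap is visible now.

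**Counts can be added by hand.** This holds across doses, because the arms are disjoint. It does not hold across preferred-term rows, where one participant can appear more than once.

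**A class effect is unproven.** Correct. Section 3.4.4.1 reports no physiologically significant hepatobiliary effect for BMS-986278, and Section 3.4.3.2 describes a 9-month monkey study without adverse drug-related findings. The documents leave the question open.

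**The trial is too small, and the predecessor signal was recognized from three events anyway.** Power is indeed low even when pooled, which argues for a descriptive table. That the earlier signal was recognized does not show that it would be again with events spread over more arms and two cohorts.

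**Conclusion.** The point holds as a gap in prespecified safety characterization. The event that ended the predecessor's development has no AESI status, no grouped term list and no combined-dose or cross-cohort summary in the plan. At the predecessor rate, the chance of seeing at least 3 events together rises from 46% in one IPF dose arm to 88% across both IPF doses and 98% across all active participants.

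These figures assume that the three events were three active-arm participants, that the predecessor rate carries over, and that all randomized participants are exposed. The rate itself is poorly known (0.6% to 8.9%); at its lower limit, even pooling gives only a 21% chance.

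A reader might also infer that zero events in 160 would rule out the predecessor's risk. It would not: the 1.9% bound lies below the 3.1% point estimate but inside the predecessor's interval. Nor do the documents show that this trial could settle whether the effect belongs to the class.

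**What to change.** **Section 9.2.5.** Add gallbladder and biliary events as an AESI, with a prespecified term list (for example cholecystitis, cholelithiasis, biliary colic, bile duct obstruction). Record cholecystectomy in its own field, because Appendix 3 treats a procedure as not itself an AE.

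**Section 10.4.3.** Add a descriptive grouped summary of participants with any listed event:
- by dose, and for both doses combined, versus placebo;
- within each cohort, and pooled across cohorts as supportive (both cohorts are 1:1:1, so active to placebo is 2:1 in each);
- with counts, risk difference and 95% CI, and no significance test.

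Add a count of participants with treatment-emergent concurrent alkaline phosphatase and total bilirubin above ULN, from tests already in Table 5. Define it relative to baseline for those elevated at entry, since exclusion criterion 3)j admits participants with Gilbert's syndrome and total bilirubin up to 5× ULN.

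If the SAP or DMC Charter already groups these events, a cross-reference in Section 10.4.3 would suffice for the table.

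**Cost.** One term list, one AESI form page, one table and a few more site queries. No dose, visit or stopping rule changes. Between-arm power stays low, so the table should be labelled as signal characterization.
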